A randomized, double-blind, placebo-controlled, parallel-group study, with balanced randomization (1:1) was designed. The study was approved by the local research committee and registered at Clinical Trial Gov (ID: NCT02731820). The participants were recruited from a cohort of postmenopausal women treated at the Radiodiagnostic Unit of Rizzoli Orthopedic Institute (IOR) from January 2016 to June 2017; periodic measurements of lumbar (at the L2–L4 level) and femoral BMD were carried out using dual-energy X-ray absorptiometry (DXA) (Discovery DXA System, Hologic Inc., Bedford, MA, USA). Written informed consent was obtained from all participants. A code was assigned to each woman at the beginning of the trial which was used to track the data throughout the study. The inclusion criteria were women with osteopenia (T-score <-1 and >-2.5) and more than 5 years post-menopause. The risk of fracture was evaluated by using the FRAX® tool [1] based on an algorithm that takes into account demographic characteristics, medical history, some clinical risk factors as well as bone mineral density (BMD) at the femoral neck. The exclusion criteria were risk of fracture (FRAX: >20 major osteoporotic fractures; >3 hip fractures), hyperkalemia, renal insufficiency, urolithiasis, use of therapies influencing bone metabolism (e.g., corticosteroids, aromatase inhibitors and estrogens), use of drugs (such as diuretics and proton pump inhibitors), calcium and potassium supplements, vitamin D, current or recent (less than three years prior to the start of the study) use of bisphosphonates, gastrointestinal disorders which hamper nutrient absorption, and mental or psychiatric disorders which precluded the possibility of correctly adhering to the protocol. All the women were interviewed regarding food habits; they followed their usual diet throughout the duration of the study. Participants were assigned to the treatment or the placebo group using a randomization sequence created by independent personnel (IOR pharmacy) using a free online tool (<http://randomization.com>) and were stratified with a 1:1 allocation using a random block size of 4.

2. Supplements

The K citrate and the placebo were kindly provided by a manufacturer (Biohealth, Turin, Italy). They were in tablet form, identical in appearance, and were packaged in bottles which were rendered anonymous (A and B) until the end of the study. The products were stored at the IOR pharmacy and dispensed according to the computer-generated randomization list. Each woman received the supplements in the corresponding prepacked bottle. Both the subjects and the investigators who followed up the participants were blinded to group assignment. All subjects had daily supplementation with vitamin D3 cholecalciferol (400 IU day $^{-1}$) and calcium carbonate (500 mg

day⁻¹). The participants assigned to the experimental group received 30 mEq K citrate daily in two tablets for oral administration; those assigned to the placebo group received the same quantity of tablets containing only the excipients. The participants had clinic visits at the time of randomization (baseline), and at 3 and 6 months. At each time point, they underwent blood and urine evaluations. The laboratory staff performing the assays was unaware of the source of the samples which were identified by numeric codes.

3. Blood Analyses

Fasting venous blood samples were collected and analyzed for creatinine, sodium, potassium, total calcium, inorganic phosphate, parathyroid hormone (PTH), and 1,25-dihydroxyvitamin D. These analytes were measured by routine methods.

4. Urine Analyses

Urine samples were collected using a standardized protocol (Lithotest®, Biohealth, Turin, Italy), and the metabolic profile was examined in an external certified lab (Lithocenter, Turin, Italy). Briefly, during collection, 24-hour (24 h) urine was aliquoted into two fractions to which 10 mL hydrochloric acid (to prevent calcium/phosphate precipitation) and 1 mL Hibitane (to prevent bacterial contamination) were added. The acidified aliquot was used to quantify calcium (Ca), citrate, magnesium (Mg), oxalate, phosphate (PO₄) and sulphate (SO₄); the Hibitane aliquot was tested for ammonium, chloride (Cl), creatinine, pH, potassium (K), sodium (Na), urea, and urate. In addition, a sample of fasting-morning urine was collected within 2 h after the 24 h collection ended, and was analyzed for citrate, calcium, urate (all expressed as creatinine ratios) and pH. Reference values were established on the basis of the assessment of mineral metabolic profile to evaluate the lithogenic risk [2,3,4]. The renal acid load was determined by calculating the 24 h urinary “potential renal acid load” (uPRAL) as follows [5]:

$$[\text{Cl (mmol day}^{-1}) + \text{SO}_4 \text{ (mmol day}^{-1}) \times 2 + \text{PO}_4 \text{ (mmol day}^{-1}) \times 1.8] - [\text{Na (mmol day}^{-1}) + \text{K (mmol day}^{-1}) + \text{Mg (mmol day}^{-1}) \times 2 + \text{Ca (mmol day}^{-1}) \times 2]$$

5. Immunoenzymatic Assay of BTM

The serum level of the bone turnover markers (BTMs) was evaluated at baseline and after 3 and 6 months of treatment. The BTM assay was carried out by following the recommended actions to minimize the pre-analytical variability [6]. The blood samples were collected after overnight fasting (between 08:00 and 10:00 a.m.), centrifuged within 2 h from collection, at 1000 g min⁻¹ for 15 min and at room temperature. The serum was transferred into cryotubes (0.5 mL of serum per cryotube)

and frozen at -80°C , within 1 h after centrifugation, until testing. The BTM serum levels were measured using commercially available reagents based on a sandwich enzyme immunoassay technique, following the manufacturer's protocols, with each sample tested in duplicate. The selected BTMs were related to (i) the number of osteoclasts (tartrate-resistant acid phosphatase 5b; TRACP5b); (ii) osteoblast function (bone alkaline phosphatase; BAP); (iii) type I collagen degradation (carboxy-terminal telopeptide; CTX); (iv) type I collagen precursor (procollagen type 1 N terminal propeptide; PINP). Source and technical notes of reagents used in this study are shown in Table 1.

Table 1. Source of the immunoenzymatic assay kits, sensitivity, precision, least significant change (LSC) and references values from healthy individuals.

Marker (Unit) Commercial name (Source)	Detection limit	Min - Max intraassay CV (%)	Min - Max interassay CV (%)	LSC (%)	Mean \pm SEM Median Min - Max		
					Female (postmenopausal)	Female (premenopausal)	Male
CTX ($\mu\text{g} \cdot \text{L}^{-1}$) Serum Crosslaps - (Immunodiagnostic systems Limited, Boldon, UK)	0.02	1.8 - 3.0	2.5 - 10.9	16.6	0.64 \pm 0.36 0.44 0.12-1.35	0.38 \pm 0.19 0.29 0.11-0.74	0.39 \pm 0.19 0.29 0.12-0.75
BAP ($\mu\text{g} \cdot \text{L}^{-1}$) Ostase BAP - (Immunodiagnostic systems Limited)	0.7	2.6 - 6.5	3.7 - 6.1	15.6	14.53 \pm 4.21 13.2 8.0-22.4	9.0 \pm 2.98 8.78 4.0-14.30	13.13 \pm 3.8 12.3 7.0-20.1
PINP ($\text{pg} \cdot \text{L}^{-1}$) Human Procollagen I N-terminal Peptide (Cusabio Technology LLC, Aachen, Germany)	18.75	8	10	29.8	22.6 \pm 1.7 ¹ 20.1 15.4-40.8		
TRACP5b ($\text{U} \cdot \text{L}^{-1}$) Bone TRAP (Immunodiagnostic systems Limited)	0.5	6.0-6.6	5.8-7.2	21.1	3.19 \pm 0.85	2.59 \pm 0.78	3.06 \pm 0.88

¹ Reference values have not been differentiated by gender and age.

6. Calculations and Statistical Analysis

All calculations and analyses were carried out using StatView 5.01 for Windows (SAS Institute Inc., Cary, NC, USA) and MedCalc Statistical Software version 18.2.1 (MedCalc Software bvba, Ostend, Belgium). The sample size calculation was based on a previous randomized clinical trial (RCT) aimed to evaluate the effect of K citrate on calcium metabolism and BTM in a cohort of individuals (males and females, age >55 years) treated for 6 months [7]. The present RCT was powered considering a Type I error (α) = 0.05 (two-sided), and Type II error (β) = 0.20 (power is 80%). Fifteen patients per group were sufficient, but the expected proportion of dropouts was 20%; therefore, as a precaution, 20 women in each group were recruited. Quantitative data were expressed as the arithmetic mean plus or minus the standard error of the mean (mean \pm SEM). The D'Agostino-Pearson method was used

to test the normality assumption of continuous variables, and a *log* transformation was applied when the data distribution was non-normal. The data analysis was carried out following intention-to-treat principles. All follow-up parameters were analyzed using a “last value carried forward” approach under the intention-to-treat principle in order to address missing data [8]. The effect of K citrate on BTMs and blood/urine analytes was evaluated by applying the *t*-test, with comparison within the groups (paired analysis of the effect of treatment over time), and between the groups (independent comparison between K citrate and the placebo at the same time point). In order to highlight the changes over time, the results were expressed in line-graphs as deviations from the value observed before treatment, i.e., $[(\text{BTM concentration at time point} \times \text{BTM concentration at baseline}^{-1}) - 1]$ Thus, obtaining a baseline value equal to zero. The degree of association between the continuous variables was calculated by measuring the Pearson correlation coefficient. Differences and correlations were considered to be statistically significant when the *p* value was <0.05 .

References

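### Randomisation is described as stratified, by factors that are not named, but the between-arm t-test has no stratum term; if prognostic strata were used, the test is conservative

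*Combined protocol and SAP*

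**What the plan says.** The opening design section of the combined protocol and SAP states that participants "were stratified with a 1:1 allocation using a random block size of 4". It attributes the list to pharmacy staff, "using a randomization sequence created by independent personnel (IOR pharmacy) using a free online tool". Neither there nor in any later section is a stratification factor, a number of strata or a set of separate lists mentioned.

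Section 6 (Calculations and Statistical Analysis) says that the effect of K citrate "was evaluated by applying the *t*-test, with comparison within the groups" and also between them, the latter being an "independent comparison between K citrate and the placebo at the same time point". No covariate or stratum term is given for the bone turnover markers or for the blood and urine analytes. The same section sets a two-sided alpha of 0.05 and 80% power, calls 15 women per group sufficient, and reports 20 recruited per group.

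**The concern.** Stratified randomisation with blocking makes the arms nearly equal on the stratification factors. Outcome differences between strata then contribute almost nothing to the random variation of the difference between arms. An unadjusted two-sample t-test does not know this. Its pooled variance still contains the between-stratum variation, so the estimated standard error exceeds the true one whenever the strata predict the outcome. Intervals are too wide, p-values too large, and precision that the design has already bought is thrown away.

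With 40 women that precision is worth having. The reader also cannot tell which of two situations applies: strata that exist but are absent from the analysis, or a word that does not describe the list. Either one calls for an edit. The within-group paired tests are not affected.

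**Working it through.** **Inputs from the document.** 1:1 allocation, stated to be stratified, block size 4 (design section). Independent-groups t-test, two-sided alpha 0.05, 20 women per group and so 40 in total (section 6).

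**Inputs that are assumptions.** The share of outcome variance explained by the strata, R². The document gives no value and names no factor, so a range of 10-30% is used. The simulation below also assumes two strata of equal expected size.

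The plan reports no figure for this point, so there is nothing of its own to reproduce. Its sample-size figures do not bear on it.

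**Step 1: standard error.** With strata balanced across arms, the true variance of the arm difference is proportional to 1 - R², while the t-test estimates it as if proportional to 1. The ratio of estimated to true standard error is 1/√(1 - R²).

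**Step 2: real type I error.** The statistic is shrunk by that ratio, so in large samples the rejection rate under no effect is 2 × P(Z > 1.96/√(1 - R²)).

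| Assumed R² | SE ratio | Effective critical value | Real type I error |
|---|---|---|---|
| 0.10 | 1/√0.90 = 1.05 | 1.96 × 1.054 = 2.07 | 3.9% |
| 0.20 | 1/√0.80 = 1.12 | 1.96 × 1.118 = 2.19 | 2.8% |
| 0.30 | 1/√0.70 = 1.20 | 1.96 × 1.195 = 2.34 | 1.9% |

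**Step 3: check at the trial's size.** The formula assumes exact balance and a normal reference distribution. A simulation of 40 women, with permuted blocks of 4 within two strata and 6,000 replicates per setting, drops both assumptions. Power is taken at a standardised difference of 0.91, the difference that a t-test with 20 per group detects with 80% power.

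| Assumed R² | Type I error, t-test | Type I error, stratum term | Power, t-test | Power, stratum term |
|---|---|---|---|---|
| 0 | 0.051 | 0.050 | 0.81 | 0.81 |
| 0.10 | 0.039 | 0.052 | 0.81 | 0.84 |
| 0.25 | 0.026 | 0.054 | 0.83 | 0.89 |
| 0.40 | 0.013 | 0.048 | 0.85 | 0.95 |

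At R² = 0.10 the simulated 0.039 matches the formula. At R² = 0.25 the formula gives 2 × P(Z > 1.96/√0.75) = 2 × P(Z > 2.26) = 0.024, against 0.026 simulated. Incomplete blocks at n = 40 therefore change little. The power given up is about 3 points at R² = 0.10 and 6 points at R² = 0.25. With R² = 0 the stratum term costs nothing visible.

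**The case against.** **No strata are shown to exist.** The claim rests on one word attached to a description of blocked 1:1 allocation. No factor is named, recruitment was at one institute, and the word may be a loose way of saying blocked. This stands. Every figure above is conditional on strata having been used, and on an R² that nothing in the document supports for an unnamed factor.

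**The error runs in the safe direction.** A reader might infer from a mismatch between randomisation and analysis that significant results are suspect. The document does not support that: if prognostic strata exist, the type I error falls below 5%. Nor does the calculation show that the planned power is missed. The unadjusted test keeps 0.81-0.85 in the simulation, and the loss is only relative to the adjusted model. Both remarks stand. They make the point minor but do not reconcile the design section with section 6.

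**A stronger reading about predictable allocation.** A reader might also infer that a single block size lets the next allocation be worked out. In complete blocks of 4, 8 of the 24 positions across the 6 balanced orders are indeed fixed by the earlier codes. The document does not support a concealment failure, for four reasons:

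- The wording reads naturally as randomly permuted blocks of size 4.
- Using the forced positions requires the block size, the block boundaries and all earlier codes, and nothing says that recruiting staff had them.
- The products were "stored at the IOR pharmacy and dispensed according to the computer-generated randomization list", the tablets looked alike, and "Both the subjects and the investigators who followed up the participants were blinded to group assignment".
- A predicted A or B label is not a known treatment.

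The one-third share also presumes a single list of complete blocks, which does not fit with stratification. That reading is not part of this point.

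**Conclusion.** The concern holds in a limited form. The document says that randomisation was stratified, and its between-arm test takes no account of strata. If strata were used and are prognostic, the t-test is conservative: for an assumed 10-30% of variance explained, the standard error is about 5-20% too large and the real type I error about 3.9-1.9%, with some power lost relative to an adjusted analysis. If strata were used but are unrelated to the outcome, nothing material changes. If none were used, the analysis needs no stratum term and the text needs correcting. Which case applies can be settled from the randomisation list, not from the document.

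**What to change.** State in the design section which factor(s), with which levels, the randomisation list was stratified by. In section 6, replace the independent t-test for every between-arm comparison (bone turnover markers, blood and urine analytes, at 3 and 6 months) with a linear model containing treatment and those factor(s) as fixed effects, and report the treatment coefficient with its 95% confidence interval. The log transformation for non-normal outcomes can stay as planned.

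If the list had no strata, delete the word stratified and keep the unstratified comparison.

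Cost: about one degree of freedom per binary factor. With 40 women and one such factor, the residual degrees of freedom go from 40 - 2 = 38 to 40 - 3 = 37. No new data are needed beyond the list and the factor values. The document is written in the past tense and the women had been recruited, so the change concerns the text and the analysis only.

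### The only bottle marking described is two shared letters, A and B; if nothing else marked the bottles, one decoded letter would reveal the arm of every other woman whose letter is known.

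*Combined protocol and SAP*

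**What the plan says.** Section 2 (Supplements) states that the potassium citrate and placebo tablets looked the same and were "packaged in bottles which were rendered anonymous (A and B) until the end of the study". On handling it says: "The products were stored at the IOR pharmacy and dispensed according to the computer-generated randomization list". Each woman then received a matching prepacked bottle; the text does not say what on the bottle made the match.

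Two kinds of individual code are described, and neither is described as a bottle label. The opening section on study design says: "A code was assigned to each woman at the beginning of the trial which was used to track the data throughout the study". Section 2 says of the assays: "The laboratory staff performing the assays was unaware of the source of the samples which were identified by numeric codes".

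On who was blinded, section 2 says: "Both the subjects and the investigators who followed up the participants were blinded to group assignment". The opening section gives two arms with 1:1 allocation, from a list made by independent pharmacy staff. Section 6 gives 20 women recruited per group. The document does not say who could see the letters, who saw urine results during treatment, or how one woman's code could be broken while the others stayed blinded.

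**The concern.** A code shared by a whole arm makes the blind all-or-nothing. With one letter per arm, learning what one letter means also gives the meaning of the other. A break for one woman, for whatever reason, then becomes a break for every woman whose letter is known to the same person.

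Shared letters also allow pooling. A single woman's results may hint only weakly at her arm, but someone who sees letters beside results for several women can compare the two letter groups. Section 4 measures analytes that could serve: "the Hibitane aliquot was tested for ammonium, chloride (Cl), creatinine, pH, potassium (K), sodium (Na), urea, and urate", and citrate in the other aliquot. The active product is potassium citrate.

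What is at stake is mainly the conduct of subjects and follow-up investigators: adherence to tablets, diet (the women were to keep their usual one) and staying in the study. The assays themselves are protected by the numeric sample codes.

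**Working it through.** **1. Women per letter.** Section 6 states that "Fifteen patients per group were sufficient" and expects 20% dropout. Inflating gives 15 / (1 − 0.20) = 18.75, so 19 per group. The stated 20 is one more, chosen as a precaution, so the plan's figure is reproduced closely enough. Two groups of 20 make 40 women, about 20 per letter.

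**2. Reach of one break.** Assume one letter per arm and no other marking. Decoding one woman's letter exposes 20 − 1 = 19 others with the same letter and 20 with the other letter: 19 + 20 = 39. This is a ceiling, reached only by someone who knows every woman's letter. With unique numbers the direct count is 0 others.

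**3. Pooling, as an illustration only.** The documents give no effect size for any urine analyte, so one has to be assumed. For a reference size, take the standardized difference that 15 per group detects at two-sided 0.05 with 80% power. The normal approximation is (1.960 + 0.842) × √(2/15) = 1.02; the t-test value is 1.06. Section 6 does not tie its 15 to an endpoint or SD, so 1.06 is a convenient size and not an estimate for urine.

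Assume one analyte, normal data and equal SD.

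- From a woman's own result at the best cut-off, P(correct arm) = Φ(d/2).
- From comparing the two letter means with n women per letter, P(both letters decoded correctly) = Φ(d × √(n/2)).

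| Assumed d (SD) | Own result | Letter groups, n = 5 | Letter groups, n = 20 |
|---|---|---|---|
| 0.5 | Φ(0.25) = 0.599 | Φ(0.791) = 0.785 | Φ(1.581) = 0.943 |
| 1.06 | Φ(0.53) = 0.702 | Φ(1.676) = 0.953 | Φ(3.352) = 0.9996 |
| 2 | Φ(1) = 0.841 | Φ(3.162) = 0.999 | above 0.999 |
| 3 | Φ(1.5) = 0.933 | about 1 | about 1 |

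A simulation at d = 1.06 agreed: 0.703 for the own result, 0.953 for n = 5 and 0.999 for n = 20.

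Pooling adds most when individual clues are weak. At 2 to 3 SD a woman's own result already gives her arm 84% to 93% of the time, so unique numbers would take away less. Step 2 does not depend on d at all.

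**The case against.** The strongest reply is that the premise is not stated. A prepacked bottle that corresponds to a woman, dispensed from a list, fits an individually labelled bottle with A and B as product codes. It fits a bare letter equally well. The text does not settle this, so the point has to stay conditional. A reader might infer that the bottles certainly carried nothing but a letter; the document describes no other marking, but does not rule one out.

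Second, the harm needs steps that are not documented. Pooling requires someone who sees letters beside results for several women during treatment. Urine went to an external laboratory, and nothing says results came back to subjects or follow-up investigators while treatment continued. The single-break route needs a break, and none is described. This stands, and it limits the weight of the point.

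Third, the safeguards are real: an independent list, pharmacy storage and dispensing, identical tablets, and assays run blind to sample source. They protect allocation, appearance and measurement. None of them stops the meaning of a letter, once known, from spreading among the people who were meant to be blinded.

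Fourth, recruitment is dated January 2016 to June 2017 and the text is in the past tense, so relabelling may come too late for this trial. That changes the remedy to a reporting one; it does not change the assessment of the scheme as described.

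**Conclusion.** The point holds in conditional form, as a cheap improvement worth making. The scheme as written uses two shared letters for two arms, and the only individual codes described serve data tracking and laboratory samples. If the letters were the only marking, one decoded letter reveals up to 39 other women, against 0 directly with unique numbers. This rests on one letter per arm, no further label, and knowledge of the other women's letters.

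Two stronger readings are tempting and should be resisted. One is that the blind failed: nothing in the document shows an unblinding, or that anyone had letters and results together. The other is that figures such as 95% or 99.96% are the chance that it failed: they are illustrations under an assumed effect and assumed access. No size can be given for any resulting bias, and no stated alpha, power or sample size changes.

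**What to change.** Label each bottle with a unique participant or kit number, with no letter shared between women, and keep the number-to-arm key only at the pharmacy. This contains a break to the woman concerned and removes the letter-group comparison. It does not stop a woman's own urine results from suggesting her arm.

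The cost is new labels before enrolment and slightly more bookkeeping at the pharmacy, which already stores the products and made the list. No extra staff, visits or participants are needed.

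If the trial is already complete, the report should state three things: whether bottles carried an individual label besides A or B, who could see the letters during the study, and whether any code was broken. That costs a few sentences.

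### Serum potassium and creatinine are evaluated only as group means, so the plan cannot show how many women on potassium citrate went above the laboratory limit and would often miss a few

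*Combined protocol and SAP*

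**What the plan says.** Section 2 (Supplements) sets the intervention: "The participants assigned to the experimental group received 30 mEq K citrate daily in two tablets for oral administration". The opening section on design and eligibility lists "hyperkalemia, renal insufficiency, urolithiasis" among the exclusions and gives no numerical limit for any of them.

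Section 2 also fixes the visits: "The participants had clinic visits at the time of randomization (baseline), and at 3 and 6 months". It adds "At each time point, they underwent blood and urine evaluations". Section 3 (Blood Analyses) names the analytes: "Fasting venous blood samples were collected and analyzed for creatinine, sodium, potassium, total calcium, inorganic phosphate", followed by PTH and 1,25-dihydroxyvitamin D.

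The analysis is in section 6 (Calculations and Statistical Analysis): "The effect of K citrate on BTMs and blood/urine analytes was evaluated by applying the" t-test, paired within each group over time and, between groups, as an "independent comparison between K citrate and the placebo at the same time point". On presentation it says: "Quantitative data were expressed as the arithmetic mean plus or minus the standard error of the mean". Last value carried forward applies to all follow-up parameters. Non-normal data are log-transformed. Pearson correlation is also planned, but for association between variables.

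No count above a limit, maximum, range or individual listing is described for serum potassium or creatinine. The reference values in section 4 concern lithogenic risk in urine, and the least significant changes in Table 1 concern bone markers.

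**The concern.** By excluding women with hyperkalemia or renal insufficiency, the plan treats high potassium and poor renal function as relevant to this intervention. It then measures both serum analytes three times. The safety question these results can answer is about individuals: did any woman go above the laboratory's limit, how many, and in which arm? A t-test answers a different question, namely whether the group averages differ.

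Two features of the plan make the mismatch worse. A few high values raise the arm's SD along with its mean, so they weaken the test that is meant to react to them. And mean ± SEM hides the spread: at n = 20 the SEM is the SD divided by √20 = 4.47, and no maximum is shown beside it.

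At stake is what the results can say about potassium. A non-significant mean comparison would read as no effect on serum potassium even if some treated women were above the limit.

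**Working it through.** **1. Group size.** Section 6 needs 15 per group and expects 20% dropout. 15 / (1 − 0.20) = 18.75, so 19; the 20 recruited per group is consistent. The check uses n = 20 per arm and two-sided α = 0.05, both from section 6.

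**2. Assumed inputs.** The documents give no potassium mean, SD, upper limit or expected rate. Assumed: mean 4.3 mmol/L, SD 0.3–0.4, k treated women raised by 1.3 mmol/L, the others unchanged, and no carry-forward. For the four tests together: within-woman correlation 0.5–0.7 and values high at both follow-up visits.

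**3. What the report would show.** With k of n women raised by d:
- mean shift = d·k/n
- variance in the active arm ≈ SD² + d²·(k/n)(1 − k/n)·n/(n − 1)

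For k = 2 and SD = 0.35:
- shift = 1.3 × 2/20 = 0.13, so the mean is 4.43
- variance = 0.1225 + 1.69 × 0.10 × 0.90 × 20/19 = 0.2826, so the SD is 0.53 and the SEM 0.53/4.47 = 0.12
- placebo SEM = 0.35/4.47 = 0.08
- t ≈ 0.13 / √(0.119² + 0.078²) = 0.91, against a critical value of 2.02 on 38 degrees of freedom

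The published line would be 4.43 ± 0.12 against 4.30 ± 0.08, not significant. For k = 3 the shift is 0.195 and t ≈ 1.27, still short.

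**4. How often the planned tests react.** Simulation with 40,000 trials per setting, counting significant increases:

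| Treated women high (of 20) | One between-group test, one visit | At least one of four tests (between and within, 3 and 6 months) |
|---|---|---|
| 0 | about 2.5% | about 8% |
| 2 | about 8–9% | about 23–25% |
| 3 | about 15–18% | about 42–45% |
| 4 | about 24–32% | about 62–74% |

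**5. Sensitivity.** With mean 4.2, SD 0.3–0.5 and affected women at 5.6, 6.0 or 6.5 mmol/L, one between-group test is significant in 3–5% of trials (1 woman), 8–10% (2), 14–22% (3) and 23–48% (4). Any of the four tests: 8–15%, 18–26%, 40–48% and 59–84%. Log transformation changes little. A more extreme value need not help: with SD 0.3, one woman at 5.6 gives 4.6% and one at 6.5 gives 3.0%.

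If the whole active arm also rises by 0.2 mmol/L, one between-group test is significant in 44–76% of trials with 2 women at 6.0, but already in 24–54% with none high. The test is then responding largely to the general shift.

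**6. What counts would give.** A count shows every measured case. Precision is low: 0 of 20 leaves an exact two-sided 95% upper bound of 1 − 0.025^(1/20) = 16.8%, and 3 of 20 gives 3.2% to 37.9%. Fisher's test of 3/20 against 0/20 gives p = 0.23, so a significance test on the counts would itself mislead.

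**The case against.** **The plan has more than one test.** Two follow-up visits, each with a paired and a between-group comparison, give four unadjusted tests. A reader who sees only the single-test figures might infer that the analysis would almost always miss a few women with high potassium. Read together, the four tests react in 42–45% of trials with 3 women high and 62–74% with 4, so that is too strong. What remains is that even a significant mean difference identifies and counts nobody.

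**Every potassium input is assumed.** This stands. The women are already selected against hyperkalemia, renal insufficiency, diuretics and potassium supplements, so the true number of high values may be small. The percentages are illustrations. That a mean cannot be turned back into a count does not depend on them.

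**No tolerability objective is stated, and counts would not settle one.** Both are true: an upper bound of 16.8% after 0 of 20 is no assurance of safety. This limits the gain to honest description.

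**Carry-forward.** One might infer that it is a main reason cases are hidden. It does give a woman who leaves before month 3 her baseline potassium, but she has no follow-up sample, so observed values would not recover her either. It also keeps a high month-3 value for a woman who leaves before month 6. What stands is the denominator: with 16 measured (20 × 0.80), 0 cases gives an upper bound of 1 − 0.025^(1/16) = 20.6%; carrying values forward would show 16.8%.

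**Silence on clinical review.** A reader might infer that nobody looked at individual results. The documents say nothing either way; the point concerns the stated analysis and reporting only.

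**Conclusion.** The point holds as a gap in analysis and reporting. For serum potassium and creatinine, section 6 states only comparisons of group means, which cannot show how many women exceeded the laboratory's upper limit. Under the assumed inputs they would often miss a few: one between-group test stays non-significant in about 91–92% of trials with 2 of 20 women high and 82–85% with 3, and all four tests stay non-significant in about 75–77% and 55–58%. These figures rest on the assumed mean, SD, size of rise and correlation.

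The documents do not support saying that high values would almost always be missed, that individual results went unreviewed, or that adverse events and dropout reasons lie ready to be tabulated: no section says these were collected. The bone-marker analysis is unaffected. The change is worth making because it costs almost nothing.

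**What to change.** In section 6, add one descriptive table for serum potassium and creatinine from the results already collected. By arm and by visit (baseline, 3 and 6 months) it should give:
- the number of women above the laboratory's own upper limit, over the number actually measured at that visit, with an exact 95% interval
- the highest observed value in each arm

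Use observed values without carry-forward, and attach no significance test. State the laboratory's limit in the table. No clinical threshold or management rule is proposed here.

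The cost is one small table, with no new visit, sample or assay. Its drawback is wide intervals, so the text should not present zero cases as evidence of safety.
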